## **Project Summary:**

Arthritis of the first metatarsophalangeal joint, otherwise known as hallux rigidus, is a common medical condition affecting approximately 2.5% of patients over the age of 50. It is a progressive disorder that leads to pain, stiffness and altered gait mechanics. While non-operative management can be successful in some patients, many will undergo symptomatic worsening that can lead to the discussion of surgical intervention. While there are multiple surgical options available, Cheilectomy has become common practice for lower grade hallux rigidus, with arthrodesis (joint fusion) being common practice for higher grade hallux rigidus. There has been a push for additional options, however, to achieve adequate pain control, with maintenance of joint motion. Multiple joint replacement type procedures have been introduced with varying levels of success. The recent introduction of a polyvinyl alcohol implant called Cartiva, has been quite promising. Multiple studies have shown the safety and efficacy of this implant used in patients with moderate and high-grade hallux rigidus. Both 2 and 5 year follow up studies have shown continued improvement in pain relief and quality of life scores, with minimal negative side effects. However, the primary outcome measures in studies up to this point have compared results between patients undergoing Cartiva implant vs. those undergoing arthrodesis. At the time of this writing, there has yet to be any investigation into patient results following cheilectomy versus Cartiva implant. While both procedures are indicated for patients with grade 2 hallux rigidus, there has not been a randomized clinical trial performed to compare these two procedures in a cohort of patients with grade 2 hallux rigidus. Furthermore, there is no data at this time as to patient characteristics that would make them a better candidate for one procedure or the other.

## **Background and Significance:**

Hallux Rigidus is a common disorder that affects an estimated 1 in 40 people over the age of 50. While debate remains about the primary cause of this disorder, it is likely multifactorial with contributing factors including previous trauma, malalignment and underlying genetic influences. Regardless of the cause, the disorder can become progressive and significantly impact a patient's quality of life. Common symptoms include pain, swelling and limited range of motion. Patients often present with pain dorsally over the first metatarsophalangeal (MTP) joint secondary to osteophyte formation and swelling. This can restrict range of motion at this joint, as well as make daily activities, such as wearing closed-toed shoes, quite difficult. Furthermore, continued pain can lead to gait abnormalities with more weight bearing through the lateral aspect of the foot and potential transfer metatarsalgia.

Along with physical exam to identify first MTP range of motion, joint swelling, erythema and palpable osteophyte formation, radiographic evaluation is part of the standard of care in hallux rigidus evaluation. Coughlin and Shurnas proposed a grading system that has become widely used, based on the radiographic findings and range of motion at the MTP joint. The grading system allowed clinicians to characterize patients from grade 0-4, helping guide treatment decisions.

Initial treatment is centered on pain relief with non-operative modalities. Modified shoe wear, custom orthotics with a Morton extension and activity modifications have all been shown to improve symptoms in some patients. For patients that fail non-operative therapies, a wide array of surgical options exist. For patients with Grade 1 and 2 hallux rigidus, joint sparing procedures have

been primarily used, with the most common procedure being Cheilectomy. The Cheilectomy procedure involves removal of the dorsal osteophytes and 20-30% of the dorsal metatarsal head. The benefits of this procedure include the ability to improve joint mobility, while still leaving the potential for future fusion. Success rates have been reported between 72% and 100% in patients with grade 1 and 2 hallux rigidus.

Joint fusion has become common place in the treatment of advanced stage hallux rigidus, including grade 3 and 4. High fusion rates and patient satisfaction has been proven with fusion procedures in the first MTP joint. However, the loss of motion at the first MTP joint associated with the fusion procedure can interfere with activities such as running and jumping, and can make shoe wear choices difficult. These limitations led to the push for development of a joint replacement procedure, allowing for pain control and continued motion.

The use of silicone-based joint replacement has been met with mixed results, however concerns over the durability leading to implant fracture, osteolysis and difficulty of revision procedures has ultimately limited its use. Ceramic implants were found to have good short-term results, however concerns remain regarding the large amount of subsidence seen in follow up, as well as potential osteolysis. Furthermore, the amount of bone stock remaining following this procedure could make revision procedures quite challenging. Given these mixed results, there remained a significant drive to identify a joint replacement-type procedure with a device that could maintain adequate bone stock, preserve motion and withstand the daily stresses the first MTP joint faces.

This led to the use of the Cartiva implant, a polyvinyl alcohol hydrogel implant. Following extensive safety and wear testing, it was determined that this implant would be well suited for use in patients with hallux rigidus. Indicated for grade 2, 3 and 4 hallux rigidus, the initial study of Cartiva effectiveness compared outcomes of the implant versus arthrodesis. The prospective, randomized control trial evaluated 202 patients, with over 2/3 undergoing the Cartiva procedure. Both short and midterm outcomes were very promising. 5-year revision rates were found to be 5% with no evidence of implant loosening or surrounding bone complication. Additionally, the Cartiva implant was found to be equivalent to the gold standard, arthrodesis, when it came to post-operative patient outcome scores, range of motion and complications.

With promising results from initial clinical trials, further evaluation into the efficacy and indications for Cartiva is necessary. To date, there is no published literature comparing Cheilectomy to Cartiva. Both procedures have shown to have beneficial results in patients with grade 2 hallux rigidus, yet these two procedures have not been directly compared in clinical trials since the invention of the Cartiva. With an estimated revision rate around 9% following Cheilectomy, it is possible that Cartiva could decrease the need for additional procedures.

#### **Specific Aims/Study Objectives:**

The major hypothesis of this study is that patient outcomes following Cartiva implantation will be non-inferior to those undergoing cheilectomy for patients with grade 2 hallux rigidus. Results will include the FAAM ADL and Sport Subscores, SF-36 scores, Visual analog pain scores and peak active dorsiflexion in the 2 patient populations. Additional results will include secondary

surgeries and adverse events. These will be evaluated pre-operatively and then post operatively at 2 weeks, 6 weeks, 3 months, 1 year and 2 year follow up. The 2 year follow up visit will be the primary end point of the study.

The primary objective of this study will be to evaluate the Cartiva procedure compared to the Cheilectomy with the above stated patient reported outcomes and physical exam measures. These two procedures are both indicated for the patient population selected in this study, however post-surgical results have never been compared to one another in current literature. The secondary objective will be to identify subsets of the study population which may be better suited for one of the two procedures. Through statistical analysis, we will attempt to identify patient variables that may impact the surgical response. This will allow surgeons to appropriately counsel their patients on which procedure they would benefit from.

### **Research Designs and Methods:**

The study will include patients with grade 2 hallux rigidus using the grading system described by Coughlin and Shurnas. Inclusion criteria will involve patients older than 18 and less than 88 years of age. These patients will have the ability to perform the questionnaires and will complete the informed consent process. Exclusion criteria will include patients with the diagnosis of gout or inflammatory arthropathy, those with inadequate bone stock of the 1st MTP joint (large bone cyst >1 cm, avascular necrosis), allergy to polyvinyl alcohol, anyone who is pregnant, anyone unable to commit to follow up appointments and patients with significant medical comorbidities that make them unsuitable for elective surgery. Subjects will be identified as having grade 2 hallux rigidus during a clinic visit with one of 3 fellowship trained foot and ankle orthopedic surgeons. After discussion of operative and non-operative interventions, patients will have the ability to decide to pursue surgery. If a patient decides to pursue surgical intervention, they will then be informed of the study. No additional subject recruitment will be performed.

Once a patient has agreed to take part in the study and has signed the informed consent, we will obtain baseline information from their medical records. This information will include gender, age, body mass index (BMI), smoking status, and prior 1st MTP joint procedures. At the patient's initial consultation visit (screening visit), their hallux rigidus grade will be defined by one of the 3 fellowship trained foot and ankle orthopedic surgeons based on the grading system from Coughlin and Shurnas. Patients will then be block randomized, by Department of Orthopedics and Rehabilitation statistician, into either one of the two treatment groups. Blocks will be 4 or 6 subjects in size to ensure balance in the two treatment arms across the duration of the study. The standard of care surgical treatment options are either Cartiva hemiarthroplasty or cheilectomy, and are the same for this study. Typically, a surgeon would have an informed discussion with the patient, listing the risks and benefits of each procedure and allow the patient to determine which procedure they would like to pursue. However, for the purpose and specific aims of this study, patients will be randomized into one of the two treatment options. Brief descriptions of the procedures are provided below:

**Cartiva hemiarthroplasty:** The procedure starts with a small incision over the top of the 1st MTP joint. The joint is exposed. Bone spurs on the metatarsal and proximal phalanx are resected, leaving approximately 2 mm of surrounding bone on the metatarsal head. A guide pin is placed within the

metatarsal and a drill is then used to create a site for the implant. The implant is then placed using the implant introducer. The incision is then closed and a sterile dressing is placed.

Cheilectomy: A small incision is made over the top of the 1st MTP joint. The joint is exposed. Bone spurs on the metatarsal and proximal phalanx are resected. The top of the metatarsal head is then cut with a sagittal saw. Additional bone spurs are resected. The incision is closed and a sterile dressing is placed.

Primary study data will be collected both pre-operatively at the patient's initial consultation visit and then again at post-operative visits at 2 weeks, 6 weeks, 3 months, 1 year and 2 years. This study data will include the following: Active peak dorsiflexion of the first MTP joint, SF-36 score, Visual analog pain score (VAS) and FAAM. This will be recorded on the attached Data Collection Form at each visit. The VAS will be performed by providing patient's with a 10 cm line and having them mark on the line where they would rate their daily pain in their 1st MTP joint. That distance from the beginning of the line will then be measured in millimeters to identify the patient's VAS score. The patient's active peak dorsiflexion will be measured in clinic with a goniometer with the patient standing and weight bearing on their operative foot. The Medical Outcomes study Short form (SF-36) has been validated and thoroughly tested for a wide range of medical conditions, including ankle arthritis, to monitor patient symptoms and responses to treatment. The questionnaire focuses on both the mental and physical aspects of a certain condition to generate composite score. The score provides the opportunity to compare patient outcomes prior to and following their surgical intervention, as well as track their progress throughout the recovery process. Finally, the Foot and Ankle Ability Measures (FAAM) questionnaire will be collected at the above stated time points. This measure has been validated for subjects with foot and ankle musculoskeletal disorders. It has also been shown to be more responsive to changes in physical functioning than the SF-36 score. At each follow up visit, the patient will be evaluated for any adverse events. If an adverse event is identified, an adverse event form (attached) will be completed. All of the above will apply to the 2 week visit, except for the administration of questionnaires/surveys. Additionally, subjects will have incision check, suture removal, and a physical completed during this visit.

Following completion by the patient at each clinical visit, the Data Collection Form will be stored in the physician's secured office in a specified folder. [name] will collect the hard copy Data Collection Forms and questionnaires and enter them into the Department of Orthopedics and Rehabilitation's REDCap Database. After data entry, the Data Collection Forms will then be stored in a secure location through the Department of Orthopedic Surgery research division, where it will be held for 7 years.

When it comes to study timeline, a patient will be given the opportunity to enroll in the study at their initial consultation visit with one of the three board certified foot and ankle surgeons. If a patient has been diagnosed with Grade 2 hallux rigidus and is a surgical candidate, they will be given the opportunity to enroll in the study. If the patient desires to participate in the study, data will be collected from them at their initial consultation visit as described in the Data Collection Form. They will then undergo surgical intervention based on their randomization. Following surgery, they will follow up in clinic at 2 weeks, 6 weeks, 3 months and 1 year following surgery. These follow up visits are standard of care and would occur regardless of patient participation in

the study. At each visit, standard of care radiographs will be taken to evaluate the first MTP joint and the VAS, SF-36 and FAAM-ADL and Sports questionnaires will be completed specifically for research. The final study visit will be at 2 years post-surgery with final radiographs and questionnaires.

	Screening	Surgery	Week 2	Week 6	Month 3	Year 1	Year 2
Informed Consent	X						
Demographics and Medical/Surgical History	X						
Data Collection Form			X	X	X	X	X
Review of Imaging			X	X	X	X	X
Physical Exam			X	X	X	X	X

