### **Statistical Considerations:**

The primary hypothesis of the study is to show that long term (2 year) functional outcomes for those undergoing Cartiva are no worse than the long term functional outcomes for those undergoing Cheilectomy. The primary outcome is the FAAM – ADL subscore from baseline to 2 years post-surgery. The MCID of FAAM-ADL is 8 units and we assume the SD of the difference in FAAM – ADL from baseline to 2 years post-surgery is near 17 units. To have 80% power in a non-inferiority test under these assumptions, we would need to recruit 57 subjects per group. For those subjects that are lost-to-follow-up or have a subsequent surgery we will impute the missing 2 year follow-up value in two ways: 1) by LOCF (last observation carried forward) and 2) by mean 2 year follow-up value for those in the same surgical group. We will then examine results from both method as a sensitivity analysis of our imputation method. To further assist in ensuring enough patients in each group we will inflate our sample size to 60 per group for a total of 120 patients.

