Primary analyses will follow the ITT principle and be based on changes in outcomes from baseline to 2 years follow-up between the two randomized groups. Statistical testing for primary analyses will consist of non-inferiority t-tests between the two groups for each numerical outcome. Secondary analyses will consist of similar non-inferiority t-tests between the two groups but at differing follow-up time points (i.e. 3 months, 6 months, and 12 months). Rates of secondary surgeries will be estimated for each group and 95% Cis will be calculated. Exploratory comparison analyses, including RM-ANOVA and log-rank survival analysis, will be examined as well to see if there were statistical differences in the various outcomes between groups. These analyses methods will be applied similarly to the secondary outcomes as well. For each patient reported outcome measure, we will use the Minimal clinically important difference (MCID) for each measure. As described above, the MCID for the FAAM-ADL subscore is 8 units. The MCID for the FAAM-Sports subscore is 9 units. The MCID for the SF-36 Physical component is estimated at 2 units for patients with lower extremity osteoarthritis conditions. The MCID for the VAS was found to be - 8 mm when evaluating patients with foot pain. Using these values, we will evaluate non-inferiority by comparing the changes from pre-operative results to the results at the described time points. Non-inferiority will be defined as differences that are less than the MCID between the Cartiva and Cheilectomy groups. Furthermore, we will assess whether patient characteristics affected the functional results between the two surgical groups by including a patient characteristic by group interaction into the statistical models.

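### The unadjusted t-test on FAAM-ADL change is valid but gives up precision: surgeon and baseline score could be adjusted for at little cost

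*Combined protocol and SAP*

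**What the plan says.** Under Research Designs and Methods, patients are identified at a clinic visit with "one of 3 fellowship trained foot and ankle orthopedic surgeons". Allocation is then described: "Patients will then be block randomized, by Department of Orthopedics and Rehabilitation statistician, into either one of the two treatment groups". Blocks hold 4 or 6 patients, and their stated purpose is to keep the two arms balanced over time. No stratification factor is named.

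Under Statistical Considerations, the primary analysis is by intention to treat on change from baseline to 2 years, using "non-inferiority t-tests between the two groups for each numerical outcome". The margin is the MCID: "Non-inferiority will be defined as differences that are less than the MCID between the Cartiva and Cheilectomy groups". For the primary outcome, "The MCID of FAAM-ADL is 8 units". The only covariate modelling planned is for interactions between patient characteristics and arm. The exploratory repeated-measures and log-rank analyses do not mention surgeon.

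Neither the list of baseline information under Research Designs and Methods nor the Data Collection Form has a field for the operating surgeon. The documents do not say how cases divide among the three surgeons, or whether each performs both procedures.

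**The concern.** Both arms are manual procedures, so the surgeon may plausibly influence the 2-year result. The surgeons also grade eligibility. Under the Data Safety and Monitoring Plan they judge whether a revision is needed, and a later operation causes the 2-year value to be imputed. Blocking over the whole trial fixes the arm totals but leaves the split within each surgeon to chance.

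If surgeons differ, their differences add to the variance of the arm comparison, and any imbalance in the realised allocation enters the estimate with no planned correction. The same applies to a chance imbalance in baseline FAAM-ADL. Precision is at stake, and so is the ease of interpreting a result that falls near the 8-unit margin. A decision to adjust made after seeing the data would be open to challenge.

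**Working it through.** **Inputs from the documents.** Margin 8 units; SD of change 17 ("ADL from baseline to 2 years post-surgery is near 17 units"); 60 patients per group planned; three surgeons. **Assumed.** One-sided alpha 0.05 (not stated), equal caseloads of 40, complete data, total SD held at 17, and surgeon means of 0/0/0, -4/0/+4 or -8/0/+8.

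**1. The plan's own figure.** The plan states: "To have 80% power in a non-inferiority test under these assumptions, we would need to recruit 57 subjects per group". With a true difference of zero, n = 2(SD/margin)²(z₁₋α + z₁₋β)².
- One-sided 0.05: 2 × (17/8)² × (1.645 + 0.842)² = 55.8, so 56. The noncentral t gives 57, with power 80.3%, and 82.1% at 60 per group.
- One-sided 0.025: 2 × (17/8)² × (1.960 + 0.842)² = 70.9, so 71 (noncentral t: 72).

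Only one-sided 0.05 reproduces 57, so it is used below.

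**2. Standard error of the planned comparison.** 17 × √(2/60) = 3.10 units.

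**3. Variance due to surgeon.** With equal caseloads and means -D, 0, +D it is 2D²/3.
- D = 4: 10.67, or 10.67/289 = 3.7% of the total.
- D = 8: 42.67, or 14.8%.

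**4. Shift from chance imbalance.** Under a 60:60 allocation that ignores surgeon, its SD is √[(2D²/3) × (2/60) × (120/119)].
- D = 4: √(10.67 × 0.0333 × 1.0084) = 0.60.
- D = 8: √(42.67 × 0.0333 × 1.0084) = 1.20.

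Simulation with blocks of 4 or 6 agrees. The 95th percentiles of its absolute size are 1.2 and 2.4 units, which are 1.2/8 = 15% and 2.4/8 = 30% of the margin. The chance that at least one surgeon has a 25:15 split or worse is about 19%.

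**5. Effect of adding surgeon.** The residual SD becomes √(289 - 2D²/3), and the standard error with surgeons balanced is that SD × √(2/60). Power at 60 per group, from simulation that allows for chance imbalance:

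| Surgeon means (assumed) | Residual SD | SE with surgeon in model | 95th percentile of shift | Power, t-test | Power, surgeon added |
|---|---|---|---|---|---|
| 0/0/0 | 17.00 | 3.10 | 0 | about 82% | 81 to 82% |
| -4/0/+4 | 16.68 | 3.05 | 1.2 | about 82% | 83 to 84% |
| -8/0/+8 | 15.69 | 2.87 | 2.4 | about 82% | about 87% |

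**6. Validity of the t-test.** In simulations with surgeon explaining 0 to 20% of the variance, the mean shift was zero to within simulation error and type I error at the margin was 4.5 to 5.5%. A 50/30/20 caseload gave nearly the same shifts as equal caseloads (95th percentile 0.9 to 2.7 units when surgeon explains 2 to 20%).

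**7. Baseline term.** Adding baseline FAAM-ADL multiplies the residual variance by about (1 - r²), where r is the correlation of change with baseline. The documents give no r, so this gain is not quantified.

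**The case against.** The strongest reply is that nothing is broken. Between-surgeon spread lies inside each arm's observed SD, so the t-test's standard error already allows for chance imbalance. An unadjusted comparison under valid randomisation is a defensible choice. This stands. A reader might infer from the missing stratification that the result is biased or the test invalid, but step 6 of the working does not support that.

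The effect sizes are also assumed. A gap of 16 units between the best and worst of three fellowship-trained surgeons is twice the MCID, and nothing in the documents supports a gap that large. This stands too, so the 2.4-unit figure is an upper scenario and not an expectation. It is also a 95th percentile, not a ceiling. Set against ordinary sampling error, the shift makes up only 0.60²/3.10² = 3.7% or 1.20²/3.10² = 15% of the variance. The 19% figure describes an allocation pattern and does no harm unless surgeons differ.

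A reader might also assume that surgeon is already known for every patient because forms are first kept in each surgeon's office. Under Data and Record Keeping those forms are collected monthly, entered in a database and moved to the research division. Temporary storage by clinic does not create an analysable variable, so the field must be added.

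Finally, imputing missing 2-year values by the surgical-group mean gives those patients no surgeon component. That weakens a surgeon term, so the power gains above, computed for complete data, are somewhat optimistic.

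What survives is that the loss of precision is avoidable, and that the plan has no pre-specified way to handle an imbalance that does occur.

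**Conclusion.** The point holds as one of efficiency and of conditional adjustment. It does not show bias, an inflated error rate or a wrong sample size; 57 and 60 per group need not change. Adding surgeon is worth between nothing and about 5 percentage points of power over the assumed range (82% to 87% at the top). The cost is under 1 point if surgeons do not differ (82.1% to 81.3% in one simulation). These figures rest on equal caseloads, total SD 17, one-sided alpha 0.05, complete data and the assumed surgeon means. The gain from baseline adjustment would come on top and cannot be sized from the documents. This is a cheap improvement; the baseline term alone is a free one, because baseline FAAM-ADL is already to be collected.

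**What to change.** In Statistical Considerations, replace the primary FAAM-ADL t-test with a linear model for 2-year change containing arm, baseline FAAM-ADL and surgeon (three levels). Judge non-inferiority from the confidence interval of the arm effect against the 8-unit margin, and state the one-sided alpha that sets its level. Keep the unadjusted t-test as a sensitivity analysis. Use the same form, each with its own baseline value, for the other numerical outcomes.

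Add one operating-surgeon field to the Data Collection Form and the database, and fill it retrospectively from medical records for anyone already treated.

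The randomisation list can stay as it is, since adjustment alone recovers most of the gain. If the sponsor prefers to stratify by surgeon, the surgeon term is still needed: in simulation, stratifying without adjusting made the test conservative (type I error 3.6 to 3.8% where surgeon explains 10 to 20% of the variance, equal caseloads). Small blocks within one surgeon are also easier for that surgeon to guess.

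Cost: a change of SAP wording, three degrees of freedom (one for baseline, two for surgeon), one data field, and a negligible loss of power if surgeons do not differ.
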